The two completed phase 3 trials support the efficacy and safety of FE 999049 (ESTHER-1 / ESTHER-2: Evidence-based Stimulation Trial with Human rFSH in Europe and Rest of World). ESTHER-1 (Trial 000004)¹ was a randomized, controlled, assessor-blind trial conducted in 11 countries in women 18-40 years undergoing IVF/ICSI followed predominantly by single blastocyst transfer. The trial was designed to demonstrate non-inferiority of FE 999049 versus an approved recombinant FSH preparation (GONAL-F) with ongoing pregnancy rate and ongoing implantation rate as co-primary endpoints and also to prospectively evaluate the outcome of an individualized FE 999049 dosing regimen based on the serum anti-Müllerian hormone (AMH) concentration (measured by Elecsys® AMH Immunoassay, Roche Diagnostics) and body weight. The ESTHER-1 trial demonstrated non-inferiority of FE 999049 to GONAL-F for ongoing pregnancy rate and ongoing implantation rate for both the per-protocol (PP) and modified intention-to-treat (mITT; randomized and exposed) populations. For the overall trial population randomized and exposed to FE 999049, the ongoing pregnancy rate was 30.7% and the ongoing implantation rate was 35.2%. Among the women aged ≥35 years, the ongoing pregnancy rate with FE 999049 was 26.9% and the ongoing implantation rate was 30.9%. ESTHER-2 (Trial 000071)² was a safety immunogenicity trial covering up to two repeated treatment cycles in subjects who did not achieve an ongoing pregnancy in ESTHER-1. The trial confirmed the low immunogenicity potential with incidences of anti-FSH antibodies after exposure to FE 999049 of 0.8% in cycle 2 and 1.1% in cycle 3, which was not higher than the incidence of 1.1% in cycle 1 (ESTHER-1) or the incidence of pre-existing anti-FSH antibodies before exposure to FE 999049, which was 1.4%. ESTHER-2 furthermore documented the efficacy of FE 999049 in repeated cycles with similar ongoing pregnancy rates between FE 999049 and GONAL-F as well as documented the safety of FE 999049 in an extended dose range up to 24 µg daily. Cryopreserved cycles using blastocysts derived from the controlled ovarian stimulation cycle in ESTHER-1 or ESTHER-2 and initiated within 1 year after start of stimulation in the subject's last stimulation cycle were followed and showed good efficacy of FE 999049 in cryopreserved cycles with an ongoing pregnancy rate of 32.3% per initiated cycle.

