6.2.1.6 Ongoing Pregnancy

If a vital pregnancy has been documented, the subject must attend a visit 8-9 weeks (56-69 days) after transfer.

The following must take place:

- Ultrasound (transvaginal or abdominal) of uterus to assess any ongoing pregnancy
- Drug accountability of estradiol and IM progesterone
- Recording of use of any concomitant medication
- Recording of adverse events

If at least one intrauterine viable fetus is identified, this confirms an ongoing pregnancy.

Trial Code: 000002 Date: 25 Apr 2018 E-Study Protocol-22377; Ver. 1.0

> Supersedes: None Page 88 of 159

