When applying the method of multiple imputation, three types of missingness are used: 1) missing the primary endpoint assessment from a recorded cryopreserved cycle because of the COVID-19 pandemic, 2) missing the primary endpoint assessment from a cryopreserved cycle that would have theoretically occurred had it not been for the COVID-19 pandemic, and 3) missing the primary endpoint assessment because of any other reason. The method of multiple imputation will only be applied to those endpoints that are missing because of the first two types of missingness. Missing endpoints because of the third type of missingness will continue to be imputed as 'negative'. If a

subject was still in the trial at the start of the COVID-19 pandemic trial hold and initiates an additional cryopreserved cycle after the end of the trial hold, but within 12 calendar months from their date of randomization, then this subject's endpoint will be considered non-missing and will not be imputed using multiple imputation.

Multiple imputation will be based on a risk-stratified hot deck imputation strategy. Subjects that are to receive imputation will be stratified by assigned treatment arm and the number of previous transfers within the study. The subjects not receiving imputation will form an imputation pool. The imputation pool will also be stratified by assigned treatment arm and the number of previous transfers within the study. If a stratum within the imputation pool contains fewer than 10 subjects, strata may be collapsed to increase the membership of a particular stratum. For each subject receiving imputation, the imputation pool will be further reduced to those subjects that have an endpoint assessment that occurred at or beyond the first date of missingness for the imputed subject's primary endpoint. Hot deck replacement commences from the reduced, stratified imputation pool 10 times, forming 10 analysis datasets from which combined estimates will be obtained using the method described by Rubin.⁵

For subjects with transfer but missing observations on the number of viable fetuses 8-9 weeks after transfer the number of viable fetuses will be imputed as zero irrespective of why data is not recorded. For subjects with transfer but missing information on the number of gestational sacs 5-6 weeks after transfer, the number of gestational sacs will be imputed as the number of viable fetuses 8-9 weeks after transfer.

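### Apart from a date filter on donors, the COVID-19 hot-deck matches only on arm and number of previous transfers; it ignores missingness type and recorded pregnancy stage

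*SAP*

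**What the plan says.** SAP 9.2.2 defines three types of missing primary endpoint. Type 1 is "missing the primary endpoint assessment from a recorded cryopreserved cycle because of the COVID-19 pandemic". Type 2 is "missing the primary endpoint assessment from a cryopreserved cycle that would have theoretically occurred had it not been for the COVID-19 pandemic". Type 3 is any other reason and stays negative. Types 1 and 2 both go to the same multiple imputation, described as a risk-stratified hot-deck with 10 replacements.

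The matching rule has three parts:
- For recipients: "Subjects that are to receive imputation will be stratified by assigned treatment arm and the number of previous transfers within the study".
- For donors: "The imputation pool will also be stratified by assigned treatment arm and the number of previous transfers within the study". Strata with fewer than 10 donors may be collapsed.
- For each recipient, "the imputation pool will be further reduced to those subjects that have an endpoint assessment that occurred at or beyond the first date of missingness" of that recipient.

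A restart rule follows. If a woman was in the trial when the hold began and starts another frozen cycle after it, within 12 calendar months of randomization, her "endpoint will be considered non-missing and will not be imputed using multiple imputation".

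In the Protocol, the endpoint scan in a programmed frozen cycle is conditional (6.2.1.6): "If a vital pregnancy has been documented, the subject must attend a visit 8-9 weeks" after transfer. Section 6.2.2.7 says the same for natural cycles. Vital pregnancy is assessed at 35-48 days (6.2.1.5, 6.2.2.6) and the endpoint scan falls at 56-69 days, so the earlier stage is on record before the later scan can be missed.

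**The concern.** Type 1 can include women with a recorded heartbeat, women with only a positive βhCG, and women with only a transfer. Their chances of an ongoing pregnancy differ widely from each other, and from the chance of a type 2 woman whose cycle had not begun. The hot-deck uses none of this. One donor pool cannot represent a vital pregnancy and an unstarted cycle at the same time, so at least one group is imputed with the wrong chance. Which group, and in which direction, depends on what *endpoint assessment* means in the date filter, and the SAP does not define it.

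The restart rule adds a smaller gap. If the restarted cycle's own scan is missed because of COVID-19, the woman meets the type 1 definition, yet she is excluded from multiple imputation. The default in 9.2.2 then scores her negative.

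At stake is the interpretability of the only planned primary-endpoint analysis that changes how pandemic-missing outcomes are imputed. SAP 11.1.1 repeats the COVID-19 sensitivity analyses for cumulative live birth, the formally tested key secondary endpoint.

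**Working it through.** **The plan's own figure.** The documents give no figure for the hot-deck. They do state at least 99% power for 30% vs 3% with 500:50 (SAP 3.2). This reproduces: 99.9995% by the pooled normal approximation at two-sided 0.05, and above 99.99% by exact enumeration of the SAP's Wald-or-Fisher rule.

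**What enters the match.** Arm, number of previous transfers, and the date of the donor's endpoint assessment. Missingness type, βhCG result, and clinical or vital pregnancy do not.

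**Can the two women share donors?** Take two women in the same arm with the same transfer count and first missing dates d1 < d2. Donors assessed at or after d2 are a subset of those assessed at or after d1. The reduced pools are nested: they overlap but need not be identical. The SAP does not say whether previous transfers include the transfer in the cycle with the missed scan. Such pairs can exist under either reading.

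**Inputs for size.**
- Donor rate across frozen cycles: the sponsor's earlier phase 3 program ended "with an ongoing pregnancy rate of 32.3% per initiated cycle" (Protocol 1.1).
- Chance of ongoing pregnancy after a heartbeat: not in the documents; assumed 0.85 to 0.97.
- Number of affected women: not in the documents; 5 is used for illustration.
- FE 999049 arm: 500 (SAP 3.2).

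**Reading A: endpoint assessment means any determined outcome of a cycle.** A heartbeat woman draws general frozen-cycle odds, about 3.2 positives in 10 draws (10 × 0.323) instead of 8.5 to 9.7.
- Shortfall per woman: 0.85 − 0.323 = 0.527; 0.97 − 0.323 = 0.647.
- Arm rate for 5 women: 5 × 0.527 / 500 = 0.53 points too low; 5 × 0.647 / 500 = 0.65 points too low.

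**Reading B: endpoint assessment means the 8-9 week scan.** That scan is due only after a vital pregnancy, so frozen-cycle donors who pass the filter are nearly all post-heartbeat. Heartbeat women are then imputed about right. A type 2 woman receives odds near 0.85 to 0.97 for a cycle whose chance from initiation is nearer 0.323. On the same inputs, and if every donor were post-heartbeat, 5 type 2 women would put the arm rate 0.53 to 0.65 points too high.

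**Wider range under Reading A.** With 0.85 to 0.95 after a heartbeat and a donor rate of 0.10 to 0.50:
- per woman, from (0.85 − 0.50) / 500 = 0.07 points to (0.95 − 0.10) / 500 = 0.17 points;
- for 10 women, 0.7 to 1.7 points.

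**Effect on the conclusion.** Lower Wald limit at the planned rates: 0.27 − 1.96 × √(0.30 × 0.70/500 + 0.03 × 0.97/50) = 0.208. With the active rate 1.7 points lower: 0.253 − 1.96 × √(0.283 × 0.717/500 + 0.03 × 0.97/50) = 0.191. Both are far above 0. (At 3% of 50, about 1.5 placebo pregnancies are expected, so the formal test would be Fisher's; the Wald limit is used here only to show scale.)

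**The case against.** The strongest case against runs as follows.

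- **A reader might infer that arm and transfer count are the whole match, so that heartbeat and unstarted women always share one donor pool.** The SAP does not support this. The date filter is applied per recipient, and two women share a stratum only if their transfer counts agree or strata are collapsed. What remains is that the filter concerns timing, not prognosis, so it does not supply the missing match.
- **A reader might infer that the plan ignores positive interim results altogether.** It does not. SAP 9.3.2 plans a sensitivity analysis that imputes ongoing pregnancy after a positive βhCG, clinical or vital pregnancy, and allows later birth or miscarriage information to be considered case by case. But the first is worded for loss to follow-up, and neither alters the hot-deck.
- **Missed scans after transfer were not the planned course.** Protocol Amendment 01 stops new frozen cycles and continues those with a transfer per protocol, so most pandemic missingness should be type 2. This stands. It makes Reading B the more consequential one, because there it is type 2 that is misimputed. The amendment also foresees women prevented from attending visits, and the SAP defines type 1 for missed assessments.
- **The size is soft.** The 32.3% comes from earlier trials with a different dosing regimen, one of which enrolled women aged 18-40; the 85-97% and the count of 5 are assumptions. This stands.
- **The error is conservative for superiority.** True under Reading A only; under Reading B it favours FE 999049.
- **Stage matching will be sparse in placebo.** True: 50 × 0.03 = 1.5 expected ongoing pregnancies, so a pooling order must be stated in advance.
- **The restart gap needs two events in sequence.** True; it is a minor wording fault, but it contradicts the type 1 definition.

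**Conclusion.** The point holds in limited form. Apart from a date filter on donors, the hot-deck uses only arm and number of previous transfers. With *endpoint assessment* undefined, it imputes either heartbeat women too low or unstarted cycles too high. The illustrative size is 0.53 to 0.65 percentage points of the FE 999049 rate per 5 women, down under Reading A and, if donors are all post-heartbeat, up under Reading B. This rests on the assumed 85-97%, the borrowed 32.3% and an assumed count.

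A reader might go further and infer that the trial's efficacy conclusion is at risk. The documents do not support that. The primary analysis scores these women negative and does not use the hot-deck, stated power is at least 99%, and a shift of 1.7 points leaves the illustrative lower limit near 19 points. What is affected is the accuracy of one supportive analysis and its repeat for live birth.

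**What to change.** Amend SAP 9.2.2 in three places.

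1. **Type 1.** Draw from donors whose frozen cycle reached at least the recipient's last recorded stage (transfer; positive βhCG; vital pregnancy), whatever happened afterwards, and whose ongoing-pregnancy outcome is known. Requiring *at least* the stage matters: donors whose last stage was a positive βhCG are by selection those who never progressed. If donors are sparse, pool over number of transfers first and, if there are still fewer than 10, over arms within stage.
2. **Type 2.** Keep arm by number of previous transfers, but state that *endpoint assessment* means any determined outcome of an initiated frozen cycle, including failure before the 8-9 week scan.
3. **Restart rule.** Treat the endpoint as non-missing only if the ongoing-pregnancy outcome of the restarted cycle is known; otherwise type 1 or type 3 applies.

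The cost is a few lines of SAP text and the matching programming; the stage variables are already collected at the scheduled visits. The downside is smaller type 1 pools and, for placebo, probable pooling across arms, which should be reported where it is used.

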9.2.2 Missing Data

Missing observations for the primary endpoint of cumulative ongoing pregnancy rate will be imputed as 'negative' irrespective of the reason why data are not recorded. Similarly, for other pregnancy endpoints (β hCG, clinical pregnancy and vital pregnancy) missing data will be imputed as 'negative' with the exception of a later observation in that cycle confirming that an earlier missing observation was in fact 'positive', e.g. in case of a missing β hCG test result and a confirmed clinical pregnancy in the same cycle then the β hCG test result will be imputed as 'positive'.

However, if a subject eligible for additional transfer chooses not to come back within the one-year period from the start of stimulation due to miscellaneous personal reasons, this is not considered a censored or missing observation due to loss to follow-up for cumulative pregnancy endpoints. Rather, the observed one-year cumulative pregnancy outcomes reflect the subject's real-life decision or circumstance.

The COVID-19 pandemic induced a trial hold where new cryopreserved cycles were not allowed to be initiated. The primary endpoint analysis is based on cryopreserved cycles initiated within 12 calendar months from the date of randomization (subsequently referred to as 12 calendar months). However, for a subset of subjects, part of their 12 calendar months will have been lost due to the COVID-19 pandemic trial hold. Therefore, the pandemic could induce missing primary endpoint information. Based on the approach outlined above, these primary endpoint assessments will be imputed as 'negative'. In order to assess the impact, if any, of the COVID-19 pandemic on the primary endpoint, additional sensitivity analyses are planned. As part of one of these additional sensitivity analyses, the primary endpoint analysis will be repeated, but with the application of multiple imputation for those endpoints missing specifically due to the pandemic.

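### On its natural reading, the hot-deck donor rule in the third COVID-19 sensitivity analysis drops women who did not return, which would push imputed success modestly upward

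*SAP*

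**What the plan says.** SAP 9.2.2 sets pandemic-related missing outcomes to negative in the primary analysis. One sensitivity analysis replaces that rule with multiple imputation (SAP 9.3.2, third COVID-19 analysis; repeated for cumulative live birth under SAP 11.1.1). Two kinds of recipient are imputed. Type 1 women have a recorded cryopreserved cycle whose outcome was lost to the pandemic. Type 2 is described as "missing the primary endpoint assessment from a cryopreserved cycle that would have theoretically occurred had it not been for the COVID-19 pandemic". All other missing outcomes (type 3) stay negative.

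The donors are built up in steps:

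- The starting set: "The subjects not receiving imputation will form an imputation pool".
- Recipients and pool are both "stratified by assigned treatment arm and the number of previous transfers within the study". Blastocysts remaining is not a stratum.
- Then, for each recipient, "the imputation pool will be further reduced to those subjects that have an endpoint assessment that occurred at or beyond the first date of missingness" of that recipient's endpoint.
- Finally, "Hot deck replacement commences from the reduced, stratified imputation pool 10 times", with results combined by Rubin's method.

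The same section says, of a woman eligible for another transfer who stays away for personal reasons, that "this is not considered a censored or missing observation due to loss to follow-up for cumulative pregnancy endpoints". Her one-year outcome is taken as observed.

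**The concern.** A donor should be someone who was in the recipient's position when the recipient's data stopped: not pregnant, with blastocysts left, in the same arm and transfer stratum. Whether the donor later came back is part of what is being imputed, so it should not decide whether she may be a donor.

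The rule appears to let it decide. Where SAP 9.2.2 describes a missing endpoint assessment it attaches the assessment to a cryopreserved cycle, and the donor's assessment must have occurred on or after a given date. A woman with blastocysts in storage who starts no further cycle has no such event. She is a true negative in the primary analysis but is unavailable as a negative donor.

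For type 2 recipients there is no matching filter. The SAP gives no rule for deciding whose cycle would have taken place, so this group may mix women who would have returned with women who would not. Drawing only from returners then gives the mixed group the success rate of returners. Imputation is within arm and few placebo women are likely to have stored blastocysts, so the effect would fall mainly on FE 999049. At stake is the credibility of one check on the COVID-19 negative rule and of its repeat for live birth.

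**Working it through.** **1. Does any text give a non-returner a later assessment?**

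- SAP 9.3 lists three ways the endpoint is determined: an ongoing pregnancy, no blastocysts left, or assessment of status in cycles begun within 12 months. A woman with blastocysts left and no further cycle meets none of these after the recipient's missing date.
- SAP 9.2.2 treats her outcome as observed but assigns it no date.
- The SAP also does not say whether the date of missingness is a calendar date or time since randomization.

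She therefore stays a donor only if a month-12 date is supplied that the SAP does not contain.

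**2. The plan's own figure, for scale.** SAP 3.2 claims at least 99% power for 30% against 3% with 500:50.

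- Pooled rate = (150 + 1.5)/550 = 0.2755
- Null SE = √(0.2755 × 0.7245 × (1/500 + 1/50)) = 0.0663
- Alternative SE = √(0.30 × 0.70/500 + 0.03 × 0.97/50) = 0.0317
- Power = Φ[(0.27 − 1.96 × 0.0663)/0.0317] = Φ(4.43) = 99.9995%

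The claim is reproduced. One-sided Fisher at 0.025 gives 99.99%, and the two-part Wald/Fisher rule gives 99.999%. The planned difference is 27 points.

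**3. Inflation from returner-only donors.** Inputs:

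- success per initiated cryopreserved cycle p = 0.323 (Protocol 1.1, earlier trials)
- FE 999049 arm 500 (SAP 3.2)
- women imputed n = 20, 40 or 60, and return probability r = 0.5 or 0.7; both are assumptions, as the documents give neither

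Expected imputed pregnancies are n × p with returner-only donors and n × r × p with the full risk set. Inflation of the FE 999049 rate = n × p × (1 − r)/500.

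| n | Returner-only | Full risk set, r = 0.5 to 0.7 | Inflation, points (r = 0.7 to 0.5) |
|---|---|---|---|
| 20 | 6.5 | 3.2 to 4.5 | 0.4 to 0.6 |
| 40 | 12.9 | 6.5 to 9.0 | 0.8 to 1.3 |
| 60 | 19.4 | 9.7 to 13.6 | 1.2 to 1.9 |

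For example, with n = 60 and r = 0.5: 60 × 0.323 × 0.5/500 = 9.69/500 = 1.9 points.

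**4. Cross-check by simulation.** Assumptions: success 20% or 32.3% per cycle; return 30% to 90%; 40% of returners not pregnant after one cycle have a second; about 7% of unsuccessful cycles reach a vital pregnancy; 10 to 50 women imputed.

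| Donors | Imputed success | Inflation against full risk set, 10 imputed | 50 imputed |
|---|---|---|---|
| Full risk set | 8% to 37% | none | none |
| Any later cycle | 26% to 41% | 0.1 to 0.6 points | 0.3 to 2.9 points |
| 8-9 week visits only | 78% to 88% | 1.0 to 1.5 points | 5.1 to 7.6 points |

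The middle row follows from p + (1 − p) × 0.4 × p. For p = 0.323 this is 0.323 + 0.087 = 0.41, and multiplying by r gives the full-risk-set value.

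**5. Could the main conclusion turn on this?** With 150/500 pregnancies on FE 999049, the one-sided Fisher p-value is 0.00001 at 2/50 on placebo, 0.023 at 8/50 and 0.048 at 9/50. The planned placebo rate of 3% corresponds to 1.5 pregnancies in 50. A shift of 1 or 2 points in the FE 999049 rate is small against that margin.

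**The case against.** The best defence is that the term is undefined and can be read harmlessly. SAP 9.2.2 says non-returners are not missing, and SAP 9.3 speaks of when the endpoint is determined. If a non-returner's endpoint is taken as determined at month 12, she and every failed cycle stay in the pool and this step causes no inflation. That makes the bias conditional. It does not dispose of the point, because that date has to be added to the SAP.

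Three further objections stand in part:

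- A date condition has a proper purpose. It removes women already pregnant or out of blastocysts before the recipient's data stopped, who are not comparable. Removing early successes lowers imputed success.
- For type 1 recipients, who had started a cycle, donors with a later cycle are the right comparison. A single donor set that includes non-returners would bias their imputed success downward.
- Type 2 recipients are by definition women whose cycle would have occurred, so returner donors would suit them if they could be identified. The SAP gives no means of doing so. That definition says who is imputed; it should not be read as the SAP's justification for the donor rule.

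A reader might go further and infer that failed transfers also drop out, since Protocol 6.2.1.6 says "If a vital pregnancy has been documented, the subject must attend a visit 8-9 weeks (56-69 days) after transfer" and other women go straight to end-of-cycle. Only near-certain successes would then be donors, and inflation would reach 5 to 8 points with 50 women imputed. The documents do not require this: nothing in SAP 9.2.2 equates an endpoint assessment with that visit, and a cycle that ends with a negative test or no vital pregnancy does settle the outcome.

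Reach is small. This is the third of three supportive COVID-19 analyses, and the first two use no hot deck. The 32.3% comes from earlier trials, one of which enrolled women aged 18 to 40, against 35 to 42 here.

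**Conclusion.** The point holds as a conditional one. On the cycle-based reading, which fits the wording best, donor eligibility depends on having returned, while type 2 recipients cannot be filtered in the same way. Their imputed success would be biased upward, mainly in the FE 999049 arm.

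The size is about 0.4 to 1.9 points on the FE 999049 rate in this analysis, given 20 to 60 women imputed, 50% to 70% return and 32.3% success per initiated cycle. The first two are assumptions and the third is carried over from other trials. The rise would be larger if only 8-9 week visits counted, and nil if non-returners were given a month-12 date.

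It would be wrong to infer that the bias is certain, that it runs to 5 points or more, or that the trial's efficacy finding is in doubt. The primary analysis sets these women to negative and does not use the hot deck.

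**What to change.** Replace the date condition in SAP 9.2.2 with a risk set in the same arm and transfer stratum, measured at the same time since randomization, and define it by type of recipient:

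- **Type 2 (no cycle started):** donors are all non-imputed women who at that time had no ongoing pregnancy and at least one blastocyst left. Use their 12-month outcome, counting non-return and failed cycles as negative.
- **Type 1 (recorded cycle):** donors are women who initiated a comparable cycle, with negative βhCG and no-vital-pregnancy outcomes kept as negatives.

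Also state the rule by which type 2 recipients are identified, so that recipients and donors are drawn from the same kind of women. Apply the same text to the live birth repeat.

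The cost is a few sentences in the SAP and no new data collection. The imputed FE 999049 rate becomes slightly less favourable.
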